6.10 Concomitant Medications

The use of concomitant medication that the investigator considers unnecessary will be discouraged in the subjects by the investigator; noncompliance with this measure could be grounds for withdrawal of the subject from the study.

Study subjects will be questioned about all concomitant medications including all herbal preparations and non-prescription medications that they are receiving, and this information will be recorded by the investigator (or designate) on the appropriate data forms.

7 MANAGEMENT AND REPORTING OF ADVERSE EVENTS/ADVERSE REACTIONS

The Principal Investigator is responsible for the evaluation and documentation of events meeting the criteria and definition of an adverse event (AE)/adverse drug reactions (ADR) or serious adverse event/reactions (SAE/SAR) as provided in this protocol.

All AEs are to be elicited by the Principal Investigator. The causality relationship of an AE with the study drug is to be determined by Principal Investigator.

Diary cards will be utilized to help subjects record and track AEs between study assessments. All adverse events/reactions on diary cards will be reviewed with subjects by the Principal Investigator and/or designate at the regularly scheduled visits. The reviewer will sign the diary card to document this review. If unable to sign the diary card, the Principal Investigator will document review of the diary card in the corresponding visit source document. If the subject is unable to attend in person, an image of the diary card will be transmitted to the Principal Investigator by photo or live video call. If possible, an image of the diary card will be printed and filed in the subject's source document file. Adverse events from the diary card will then be entered into the electronic case report form (eCRF) that is within data capture (EDC) system.

All adverse events/reactions will be examined by the investigator for assessment of both severity and causality using the criteria described in sections [7.6](#) and [7.7](#).

The definitions for adverse events/adverse drug reactions, as well as serious events/reactions provided below follow definitions provided by ICH, 21 CFR 312 and Office for Human Research Protection (OHRP) Guidance documents.

7.1 Adverse Events

An AE is defined as any untoward medical occurrence associated with the use of a drug in humans, whether or not considered drug related as per 21 CFR 312.32.

An AE can therefore be any unfavorable and unintended sign including an abnormal laboratory finding, symptom, or disease temporally associated with the use of ACAM2000, whether or not it is considered related to ACAM2000.

Examples of AEs include:

- Exacerbation of a chronic or intermittent pre-existing condition, including either an increase in frequency or intensity of the condition including an existing sign or symptom (i.e., worsening).
- Significant or unexpected worsening or exacerbation of the condition/indication under the study.
- A new condition detected or diagnosed after ACAM2000 administration even though it may have been present prior to the start of the study (congenital anomalies diagnosed after ACAM2000 administration would not be considered an AE).
- Signs, symptoms, or clinical sequelae of a suspected overdose of either ACAM2000 or a concurrent medication (“overdose” per se, should not be reported as an AE/SAE).
- Pre- or post-treatment events that occur as a result of protocol-mandated procedures.

An AE does not include:

- Expected vaccination reactions that are mild in nature (see section 7.8.1).
- Medical or surgical procedures (e.g., colonoscopy or biopsy) occurring while on study; the medical condition that leads to the procedure is considered an AE.
- Social or convenience hospital admissions where an untoward medical occurrence did not occur.
- Day-to-day fluctuations of a pre-existing disease or conditions present or detected at the start of the study that do not worsen.

Any AEs that are considered serious (section 7.5) (SAEs) must be reported to Emergent either by fax or E-mail according to section 7.10.

The safety information to be collected includes the nature, date and time of onset, intensity, duration, causality, and outcome of the event. Even if the AE/SAE is assessed by the physician and/or healthcare provider as not reasonably attributable to ACAM2000, its occurrence must be recorded in the source documents and into the EDC.

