6.4 Post-vaccination Day 7 (± 1)

- Identify if any exclusion criteria have arisen (i.e. skin conditions, living conditions/close contacts, pregnancy).
- Assessment of pericarditis/myocarditis symptoms (see section [6.9](#)).
- Urine pregnancy test [females of childbearing potential (must be negative)]. In the event of a positive pregnancy test result, the pregnancy must be reported to Emergent and the *National Smallpox Vaccine in Pregnancy Registry*. As a COVID-19 precautionary measure, women of childbearing potential will not be included in the study temporarily.
- Vaccination site inspection (see section [6.3](#)). If the visit cannot be performed in person, the study subject should take a photograph of the vaccination site or show it over live video call to the Investigator who will document the assessment. Photo or video will be deleted after assessment.
 - If subject does not have a cutaneous reaction (presence of induration, erythema and/or a characteristic papule lesion) at the vaccination site by Day 7, there is no confirmation of vaccination 'take'. As these subjects do not develop an immune response to the vaccination and are unlikely to be at risk of vaccination complications, further follow-up will be conducted by phone on Day 12 and Day 28. These non-responder subjects are not eligible for plasmapheresis. All non-responders will attend End of Study (Day 35 ± 3) visit in person at the site. For non-responders no Final Safety Assessment at Day 90 (± 3) will be necessary. All female subjects of childbearing potential must undergo a urine pregnancy test at Day 35 post-vaccination, regardless of 'take' status. As a COVID-19 precautionary measure, women of childbearing potential will not be included in the study temporarily.
- Unanticipated problems.
- All adverse events including all cardiovascular adverse events (symptoms and signs).
- Diary card review and verification against AE collection above.
- Concomitant medications (see section [6.10](#)).
- Review vaccination site care instructions and provide vaccination site dressing kit (see section [6.2.3](#)).

6.5 Post-vaccination Weekly Follow-ups Days 12 (± 2), 21 (± 3), 28 (± 3) and Plasmapheresis

Plasmapheresis must not begin until at least 10 days after ACAM2000 vaccination. Donors will undergo plasmapheresis according to FDA approved site procedures.

Although plasmapheresis may occur up to biweekly during this period, the following study assessments will only be required once per week:

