7.4 Adverse Events of Special Interest

Adverse events of special interest that need to be reported to the sponsor are: autoinoculation, cardiomyopathy, central nervous system disease, contact transmission of vaccinia, death, eczema vaccinatum, fetal vaccinia, generalized vaccinia, ischemic heart disease, ocular vaccinia, potential myocarditis and pericarditis, progressive vaccinia, Stevens-Johnson Syndrome, and superinfection of vaccination site.

These events can be non-serious and unrelated to the product.

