7.5 Serious Adverse Events

An AE should be classified as a SAE if it meets one of the following criteria:

- Results in death.
- It is life-threatening. An event is considered life-threatening if, in the view of the physician or healthcare provider, its occurrence places the subject at immediate risk of death at the time of the event; it does not refer to an event that hypothetically might have caused death if it was more severe.
- Requires inpatient hospitalization or prolongation of existing hospitalization.

Note: complications that occur during hospitalization are AEs. If a complication prolongs hospitalization or fulfills any other serious criteria, the event is considered serious. Any stable condition for which hospitalization is planned before study inclusion or in-hospital treatment as outpatient is not considered an SAE. Hospitalization during the study for social reasons (transport difficulties, respite, etc.) or observation in the emergency room for no more than 24 hours is not considered an SAE.

Emergency room visits that do not result in admission to the hospital should be evaluated for one of the other serious outcomes (e.g., life-threatening; required intervention to prevent permanent impairment or damage; other serious medically important event).

- Results in persistent or significant disability or incapacity. The term disability is defined as substantial disruption of a person's ability to conduct normal life functions, physically or mentally. This definition is not intended to include experiences of relatively minor medical significance, such as uncomplicated headache, nausea, vomiting, diarrhea, influenza, or accidental trauma (e.g., sprained ankle) that may interfere with or prevent everyday life functions but do not constitute a substantial disruption.
- Constitutes a congenital anomaly or birth defect.
- Any other medically significant event. Any other medically significant event includes an important medical event that may not be immediately life threatening or result in death or hospitalization but may jeopardize the subject and may require medical or surgical intervention to prevent one of the other outcomes listed in the definition above. Examples of such events include intensive treatment in an emergency room or at home for allergic bronchospasm; blood dyscrasias or convulsions that do not result in hospitalization; or development of drug dependency or drug abuse.

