14.3.4.3 Summary of out-of-range blood chemistry test results

¹ This table will be generated if at least one adverse event is experienced by at least 5% of subjects.

² This table will only be generated if a sufficient number of SAEs are recorded.

- 14.3.4.4 Summary of out-of-range hematology test results
- 14.3.4.5 Summary of incidence of abnormal EKG results
- 14.3.4.6 Summary of vital signs over time
- 14.3.4.7 Summary of pregnancy test results

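### Read literally, Protocol 7.1 conflicts with the birth-defect SAE criterion in 7.5, and neither document plans how the outcome of a reported pregnancy is obtained

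*Protocol*

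**What the plan says.** **AE definition (Protocol 7.1).** One of the examples of an AE is: "A new condition detected or diagnosed after ACAM2000 administration even though it may have been present prior to the start of the study". A parenthesis attached to it adds that "congenital anomalies diagnosed after ACAM2000 administration would not be considered an AE".

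**SAE definition (Protocol 7.5).** The section opens: "An AE should be classified as a SAE if it meets one of the following criteria". One criterion is: "Constitutes a congenital anomaly or birth defect".

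**AESIs (Protocol 7.4, 7.9 and 7.10).** The list includes "contact transmission of vaccinia, death, eczema vaccinatum, fetal vaccinia, generalized vaccinia", and 7.4 adds: "These events can be non-serious and unrelated to the product". Section 7.10 asks for a phone report within 24 hours of the site's knowledge and an SAE Form within three calendar days.

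**Pregnancy (Protocol 6.4 to 6.7).** "In the event of a positive pregnancy test result, the pregnancy must be reported to" the sponsor and a national registry for smallpox vaccine in pregnancy. The Schedule of Events has pregnancy tests from screening to Day 35 and at any extended weekly visits, but none at Day 90.

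**Analysis (SAP 6, 7 and Appendices I and III).** The pregnancy outputs are "14.3.4.7 Summary of pregnancy test results" and Listing 16.2.8.3, which covers childbearing potential and test results. Under SAP 7, one pregnancy starts a sponsor investigation and two call an ad hoc DSMB meeting.

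**The concern.** There are two linked problems.

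First, an SAE under 7.5 must already be an AE. An anomaly in a child exposed in utero through vaccination can only be diagnosed after administration. If an investigator applies the 7.1 parenthesis as worded, that anomaly is not an AE and the birth-defect criterion is never reached.

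Second, the plan tests repeatedly for pregnancy and reacts when one is found, but neither document says how its outcome is learned or where it is recorded.

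Donor safety is the objective the SAP analyses. Protocol 7.8 records fetal death after both primary vaccination and revaccination, and every subject here is a revaccinee. SAP 7 gives fetal vaccinia and fetal death as the background to its pregnancy trigger. As planned, the study would count a pregnancy without a defined way of knowing whether the harm behind that trigger occurred.

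**Working it through.** The plan gives no figure to reproduce. The check is a comparison of texts plus one timing illustration.

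**1. Protocol 7.1 against 7.5**
- 7.5 makes SAEs a subset of AEs.
- 7.5 makes a congenital anomaly or birth defect serious.
- 7.1 says an anomaly diagnosed after administration is not an AE.
- Read literally, an anomaly in exposed offspring is diagnosed after administration, so it is not an AE and cannot be an SAE.
- Read in context, the sentence that carries the parenthesis concerns a condition of the subject that may predate the study. The exclusion then covers the vaccinee's own congenital condition found late, and 7.5 is untouched. The parenthesis does not state this limit in words.

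**2. What happens after a positive test**

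| Step | What the documents provide | Reaches the outcome? |
|---|---|---|
| Report to sponsor and registry (Protocol 6.4 to 6.7) | Notification of the pregnancy | Not stated; no return of registry data is described |
| Day 90 contact (Protocol 6.8) | No test; pregnancy asked about only if the scab is still attached | No |
| Non-responders (Protocol 6.4) | No Day 90 contact; last visit is Day 35 | No |
| Follow-up after the final visit (Protocol 7.9) | Related AEs only; pregnancy is not defined as an AE | No |
| AESI report (Protocol 7.4, 7.10) | Fetal vaccinia and death, once the site knows; congenital anomaly is not listed | Only if the site learns of it |
| Sponsor investigation and DSMB trigger (SAP 7) | Set off by the pregnancy itself | Not stated |
| SAP Table 14.3.4.7 and Listing 16.2.8.3 | Test results and childbearing potential | No |

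The AESI list does not say whether death includes fetal loss; SAP 7 names fetal death separately.

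**3. Timing illustration**

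Assumptions, neither in the documents: 266 days from conception to term birth, and conception between 14 days before vaccination (too early to detect) and Day 35.

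Birth day = conception day + 266
- Earliest: -14 + 266 = Day 252
- Latest: 35 + 266 = Day 301

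Gap after the Day 90 contact = birth day - 90
- Earliest: 252 - 90 = 162 days
- Latest: 301 - 90 = 211 days

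For a non-responder, gap after Day 35 = birth day - 35
- Earliest: 252 - 35 = 217 days
- Latest: 301 - 35 = 266 days

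Under these assumptions no scheduled contact can observe a term birth. An early loss can fall before Day 90.

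**The case against.** The strongest reply is that the host sentence supplies the limit. The parenthesis sits in the list of examples of AEs, not in the separate list of what an AE does not include, and it qualifies a condition of the subject that may predate the study. Section 7.5 keeps the birth-defect criterion, and Section 7 says the definitions follow ICH and federal rules. This stands as a reading of intent. A reader might infer that 7.1 cancels the 7.5 criterion, but the documents do not support that. What remains is unqualified wording that conflicts with 7.5 if taken at face value.

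A reader might also infer that fetal harm cannot enter the safety data at all. That is not supported either:
- Fetal vaccinia and death are AESIs even when non-serious or unrelated.
- Related AEs may be followed beyond Day 90 (Protocol 1.2).
- Unanticipated problems cover increased risk to people other than subjects (Protocol 7.11).
- One related SAE calls an ad hoc DSMB meeting, and SAP 14.3.2 and 14.3.3 list and narrate deaths and other SAEs.

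These routes work once someone at the site knows of the event. None of them obtains the outcome after the last scheduled contact.

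Finally, the sponsor's investigation of a single pregnancy follows a Medical Monitoring Plan that is not available here, and the registry may hold outcomes. So one cannot say that no outcome is collected anywhere, only that the protocol and SAP do not describe it.

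**Conclusion.** The concern holds in two limited parts. The 7.1 parenthesis conflicts with 7.5 on a literal reading and should be reconciled with it, although its likely intent is narrow. Separately, neither document gives a planned route from a reported pregnancy to its outcome in the study data.

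The likely number of affected subjects is small, but the documents give no pregnancy rate. The two-pregnancy DSMB trigger is a threshold, not an expected count. Women of childbearing potential are temporarily not included under the current protocol; otherwise contraception and repeated testing limit exposure. Women vaccinated before that measure, or after it is lifted, are still affected.

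For each such pregnancy, a term birth would come about 162 to 211 days after Day 90. This rests on the assumed 266-day gestation and conception window, and does not apply to early losses. Correcting the rule and following these pregnancies is worth doing because it changes what the safety data can show at very small cost.

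**What to change.** 1. **Protocol 7.1:** limit the parenthesis to a congenital anomaly of the subject that was present before vaccination. An anomaly in exposed offspring then falls under the 7.5 criterion and the 7.10 reporting route.
2. **Protocol 6.4 to 6.8 and 7.10:** state that each reported pregnancy is followed to its outcome (live birth, loss or anomaly) and recorded on one eCRF page. If the registry or the sponsor's investigation already obtains the outcome, say so and say how it returns to the study database.
3. **SAP Listing 16.2.8.3:** add the outcome.

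The cost is one phrase, one eCRF page, one added item in a listing, and a later contact for each pregnancy. The downside is that a few records stay open past Day 90.

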7.2 Adverse Drug Reaction(s) (ADRs)

An adverse drug reaction is defined as an unwanted noxious and unintended response to a therapeutic drug. ADRs are characterized by a suspected causal relationship between the product and the occurrence of the reaction.

The phrase "unwanted noxious and unintended response" means that a causal relationship between the medicinal product and the onset of an adverse event is at least a reasonable possibility, i.e., the relationship cannot be ruled out.

Causal relationships should be assessed according to section 7.7.

7.3 Expected/Unexpected AEs/ADRs

An expected adverse drug reaction/event is an adverse reaction/event that is consistent by nature or severity (see section 7.6), specificity, or outcome with the *Investigator's Brochure*.

An expected ADR with a fatal outcome should be considered unexpected unless the *Investigator's Brochure* specifically states that the ADR might be associated with a fatal outcome.

An unexpected adverse drug reaction/event is an adverse reaction/event that is **not** consistent by nature or severity (see section 7.6), specificity, or outcome with the *Investigator's Brochure*.

7.4 Adverse Events of Special Interest

Adverse events of special interest that need to be reported to the sponsor are: autoinoculation, cardiomyopathy, central nervous system disease, contact transmission of vaccinia, death, eczema vaccinatum, fetal vaccinia, generalized vaccinia, ischemic heart disease, ocular vaccinia, potential myocarditis and pericarditis, progressive vaccinia, Stevens-Johnson Syndrome, and superinfection of vaccination site.

These events can be non-serious and unrelated to the product.

7.5 Serious Adverse Events

An AE should be classified as a SAE if it meets one of the following criteria:

- Results in death.
- It is life-threatening. An event is considered life-threatening if, in the view of the physician or healthcare provider, its occurrence places the subject at immediate risk of death at the time of the event; it does not refer to an event that hypothetically might have caused death if it was more severe.
- Requires inpatient hospitalization or prolongation of existing hospitalization.

Note: complications that occur during hospitalization are AEs. If a complication prolongs hospitalization or fulfills any other serious criteria, the event is considered serious. Any stable condition for which hospitalization is planned before study inclusion or in-hospital treatment as outpatient is not considered an SAE. Hospitalization during the study for social reasons (transport difficulties, respite, etc.) or observation in the emergency room for no more than 24 hours is not considered an SAE.

Emergency room visits that do not result in admission to the hospital should be evaluated for one of the other serious outcomes (e.g., life-threatening; required intervention to prevent permanent impairment or damage; other serious medically important event).

- Results in persistent or significant disability or incapacity. The term disability is defined as substantial disruption of a person's ability to conduct normal life functions, physically or mentally. This definition is not intended to include experiences of relatively minor medical significance, such as uncomplicated headache, nausea, vomiting, diarrhea, influenza, or accidental trauma (e.g., sprained ankle) that may interfere with or prevent everyday life functions but do not constitute a substantial disruption.
- Constitutes a congenital anomaly or birth defect.
- Any other medically significant event. Any other medically significant event includes an important medical event that may not be immediately life threatening or result in death or hospitalization but may jeopardize the subject and may require medical or surgical intervention to prevent one of the other outcomes listed in the definition above. Examples of such events include intensive treatment in an emergency room or at home for allergic bronchospasm; blood dyscrasias or convulsions that do not result in hospitalization; or development of drug dependency or drug abuse.

7.6 Assessment of Severity (intensity)

Assessments of AE/ADR severity are to follow the guidelines provided below:

Table 1 AE/ADR Severity Assessment

Intensity	Description
Mild	Awareness of a sign or symptom but subject can tolerate.
Moderate	Discomfort enough to cause interference with normal daily activity.
Severe	Resulting in an inability to do work or do usual daily activity.

7.7 Assessment of Causality

Causality is an established relationship between the occurrence of an adverse event/reaction and the concomitant or previous intake of medications.

Adverse events may be caused by one or more of the following:

1. The product and/or procedures involved in the research study.
2. An underlying disease, disorder, or condition of the subject.
3. Other circumstances unrelated to the research or any underlying disease, disorder, or condition of the subject.

In general, adverse events that are determined to be at least partially caused by (1) would be considered related to participation in the research, whereas adverse events determined to be solely caused by (2) or (3) would be considered unrelated to participation in the research.

The various causality categories are listed in Table 2.

Table 2 General Definitions of Causality Categories

Certain (Definitely Related)	
 Event or laboratory test abnormality, with plausible time relationship to the study drug intake Cannot be explained by disease or other drugs Response to withdrawal plausible (pharmacologically, pathologically) Event definitive pharmacologically or phenomenologically (i.e. an objective and specific medical disorder or a recognized pharmacological phenomenon) Rechallenge satisfactory, if necessary
Probable (Probably Related)	
 Event or laboratory test abnormality, with reasonable time relationship to drug intake Unlikely to be attributed to disease or other drugs Response to withdrawal clinically reasonable Rechallenge not required
Possible (Possibly Related)	
 Event or laboratory test abnormality, with reasonable time relationship to drug intake Could also be explained by disease or other drugs Information on drug withdrawal may be lacking or unclear
Unlikely	
 Event or laboratory test abnormality, with a time to drug intake that makes a relationship improbable (but not impossible) Disease or other drugs provide plausible explanations
Unrelated	
 No temporal association to study product. An alternate etiology has been established. The event does not follow the known pattern of response to study product. The event does not reappear or worsen with re-challenge.
Conditional/ Unclassified ^a	
 Event or laboratory test abnormality More data for proper assessment needed, or Additional data under examination
Unassessable/ Unclassifiable ^a	
 Report suggesting an adverse reaction Cannot be judged because information is insufficient or contradictory Data cannot be supplemented or verified

^a This is a temporary assessment to be used within the initial SAE report, since stringent timelines might not allow the collection of all the information necessary for making proper causality assessment. In this case, investigators must actively seek all available data on the event and provide a causality assessment of certain (definite)/ probable/ possible/ unlikely in a follow-up SAE report.

